2.10 Data management

Human subject demographic and clinical metadata will contain confidential and personal information. Case report forms (CRFs) will be entered digitally on password encrypted tablets using the electronic data capture (EDC) system ODK, then transferred daily to the SQL server, a password encrypted database, using a secure connection at MLW in

NP Resistome Study

Version 5.0 21/05/2025

Page 20 of 30

compliance with Malawian data transfer legislation. Only trained study field team members will have access to this encrypted database; access will be controlled by unique user ID and password setup to maintain confidentiality. Data entry, modification, and download will be restricted to specific roles in the study team. All password encrypted tablets will be locked in a secure location when not in use on field visits. Data cleaning and database locking will be conducted at MLW. The database will be locked shortly after study completion; anonymised data will then be transferred via the MLW data portal to a password encrypted folder on the LSTM shared (S:) network drive and a password encrypted external hard drive.

Paper documents will be used for recording the process of data collection in the laboratory; a member of study staff will deliver paper documents to a data centre with locked cabinets. Study documentation, including consent forms, will be archived in-country for 10 years, as per LSTM policy.

NPS and urine samples will be labelled with a barcode linked to a unique identifier, which will be recorded on the CRFs during data entry. Metagenomic sequence data will be labelled with this unique identifier. Raw metagenomic sequence data will contain confidential human genome sequence data; this will be removed in the bioinformatic pipeline and not stored long-term.

2.11 Data sharing and access

Access to the study database and metagenomic sequence data will be restricted to the clinical study team, or approval granted by the principal investigator (PI), to ensure participant confidentiality.

No human genome sequence data will be shared with researchers. Anonymised human genome, microbiome and resistome sequence data will be stored in .fast5, .fastq and .csv format on a password encrypted folder on the LSTM shared (S:) drive space, a password encrypted external hard drive and in the Amazon Elastic Compute Cloud, a secure web platform for data storage.

As a population health study, anonymised digital patient and metagenomic data will be stored on password-encrypted external hard drives for a minimum of 10 years after study completion; these will be retained by the PI and clinical fellow at LSTM. Open access publication and sharing of curated metagenomic data on the github repository will ensure long-term data preservation. All electronic databases will be stored behind institutional firewalls, backed-up on-site and off-site according to standard operating procedures (SOPs).

NP Resistome Study

Version 5.0 21/05/2025

Page 21 of 30

This will be overseen by the investigators. The processes and specific details of data sharing and access will be described in the Data Management and Access Plan.

2.12 Quality assurance and quality control

To ensure the quality of processes, data and documentation, a manual of procedures (MOP) will be prepared. This will encompass both quality control (QC) and quality assurance (QA) activities, with SOPs to ensure confidentiality and data integrity and to prevent human and processing errors. Key elements covered by the SOPs will include:

- Data storage: Utilization of unique participant identification numbers for data storage.
- Data Evaluation: Ensuring protocol compliance and source document accuracy.
- Document Review: Establishing responsibilities and frequency for document review, including specimen tracking logs and questionnaires.
- QA and QC Issue Resolution: Outlining responsibilities for addressing QA issues (correcting procedures not compliant with the protocol) and QC issues (correcting errors in data entry).

During study conduct, the MLW Clinical Research Support Unit may look closely at field data quality, specimen quality and laboratory examination processes. In the event of identifying a protocol deviation, documentation must include a detailed description, root cause analysis, plan for correction and prevention of future deviations. Any deviations to the protocol will be submitted to LSTM as sponsor; any proposed amendments to the protocol will be submitted to LSTM as sponsor and the LSTM research ethics committee (REC) for approval.

2.13 Dissemination of the results

The study results will be shared with COMREC and the Ministry of Health after study completion and data analysis. All research outputs from this study will be published on open-source platforms or in open-source scientific journals. I will work with the VacAMR CEI team to share our findings with participating communities and local stakeholders at QECH, to ensure research outputs benefit the local population. I will also communicate our findings to patients and the public in Malawi and globally, to generate a wider dialogue around AMR, through collaborations with non-governmental organisations such as One Health Trust, The Foundation to Prevent Antibiotic Resistance, Antibiotic Research UK and the British Society for Antimicrobial Chemotherapy. I will create public information bulletins that summarise our findings, to improve accessibility to key information.

NP Resistome Study

Version 5.0 21/05/2025

Page 22 of 30

2.14 Ethical considerations

Written study information and consent material will be provided in Chichewa. Consent for participation in this observational study will be sought from the legal guardians of participants, as our study population aged 12-24 months will not be able to consent for themselves. The consent process will detail the collection of NPS for metagenomic sequencing and viral PCR, urine samples for antibiotic assays and recording of demographic data, co-morbidities and health outcomes for analysis. The consent process will explain that anonymised microbiome and resistome data will be shared with other researchers. No human genome sequence data will be shared.

Study participants will be renumerated for study visits in keeping with current guidance [29]. Study visits and nasopharyngeal sampling from children will be minimised to ensure participant retention.

2.14.1 Ethical compliance

The study protocol will be reviewed and approved by COMREC and LSTM REC. Any amendment will require COMREC and LSTM REC approval before implementation; any amended protocol would then supersede the initial protocol. Prior to study enrolment, parents/legally acceptable representative s of study participants will be provided with all necessary information about the study and voluntary study participation. Written informed consent will be sought and documented from at least one parent/legally acceptable representative of all study participants. The study will be conducted in compliance with the protocol and applicable global and local ethical requirements.

2.15 Project risks and constraints

Potential challenges to study completion and risks of participant enrolment are considered below.

2.15.1 Failure to recruit sufficient participant numbers

A major potential challenge to study completion is identifying enough participants being re-hospitalised within 3 months to meet our recruitment targets. There is no data on hospital re-admission rates due to pneumonia in Sub-Saharan Africa. The leading cause of recurrent hospitalisation among children aged under 5 years in Sub-Saharan Africa is severe anaemia, with a readmission rate of 18% over 6 months [27]. A study conducted at QECH between April 2013 and August 2016 recruited 1600 children presenting with pneumonia that met the WHO's Integrated Management of Childhood Illness (IMCI) definition: cough or

NP Resistome Study

Version 5.0 21/05/2025

Page 23 of 30

difficult/fast breathing [30]; this is broader than our clinical definition, but based on this we could expect to recruit approximately 500 children hospitalised with pneumonia in a 12-month period. If the hospital re-admission rate were equal to severe anaemia at 18% over 6 months, this would equate to just 90 cases in a 12-month period.

A 4-week audit of hospital re-admission rates of children aged 12-24 months with pneumonia will be conducted at QECH before starting study recruitment, to further inform sample size calculations. We will use parent/carer reporting and patients' health passports as screening tools to identify those being re-admitted within 3 months of a previous hospitalisation with pneumonia. Our budget includes a stipend for hospital nursing staff to identify potentially eligible patients for screening during the admission process.

If the study experiences low participant enrolment numbers within the first 4 months, we will reassess and renew our CEI activities. Potential adjustments to the study design could include a wider age-range of study participants, although this would likely result in greater variability of baseline NPM and NPR; modifying the case to control ratio to 0.75 to 2; or adjusting the case definition to include hospital re-admissions with any infection requiring antibiotics within 3 months of hospitalisation with pneumonia, which may enable us to capture the extra-pulmonary adverse health effects of AMR.

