1.3.3 Specific Secondary Objectives

- 1. To measure the rate of hospital re-admission with pneumonia in children aged 12-24 months over a 4-week period in a single tertiary referral hospital in Malawi.
- 2. To measure antibiotic use in the community in children aged 12-24 months in Malawi.

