excluded from this control group, to prevent confounding. Children admitted to QECH with pneumonia within 3 months of a previous hospital admission with pneumonia will form the case group; these participants will have a NPS collected at the first study visit (within 24 hours of admission) only, to assess for a hospital-acquired resistome. Health passport screening and carer-reporting will be used to establish prior hospitalisation.

A 4-week audit of hospital re-admission rates of children aged 12-24 months with pneumonia will be conducted at QECH before starting study recruitment, to further inform sample size calculations.

[figure not shown]

Figure 2. Case-control study design to examine whether a hospital-acquired NPR is associated with re-admission to hospital with pneumonia.

Two flocked NPS will be taken at the first study visit from all study participants; one NPS will be stored for viral PCR analysis (outside this fellowship), the other NPS will undergo metagenomic sequencing. Viral PCR analysis of the NPS will seek to identify RNA pathogens most associated with severe acute respiratory infections requiring hospitalisation in this population: Respiratory Syncytial Virus (RSV) and Influenza A [19]. Only one NPS for metagenomic sequencing will be taken from study participants at subsequent study visits e.g. discharge from hospital and 3-month follow-up. All NPS will be stored at -80°Celsius, following an established protocol [20], prior to DNA extraction using mechanical and chemical lysis to optimise the yield of DNA from low-biomass samples dominated by grampositive organisms. Extracted DNA will undergo metagenomic sequencing. Metagenomic data analysis will be performed using an open-source bioinformatic pipeline that I will develop to determine NPM and NPR composition. A urine sample will also be collected from

NP Resistome Study Version 5.0 21/05/2025

Approved by
College of Medicine

16/06/2025

(COMREC)
Research and Ethics Committee

Page 12 of 30

each participant at the first study visit, and stored for antibiotic assays (outside this fellowship), to assess the impact of antibiotic use prior to seeking healthcare input on NPR composition.

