2.5 Sample size and calculations

There is no established method for sample size calculation in resistome studies; we use an approach for microbiome studies [25]. Differences in gut plasmidome composition have been detected with 41 participants per group [26], but NPR has a lower biomass than gut resistome, therefore the resistome is likely to be less diverse, with a lower relative abundance of ARGs. NPR analysis 3.5 years post-antibiotic exposure in a cluster-randomised trial of mass-azithromycin administration shows a trend toward decreased NPR diversity (p = 0.07) in azithromycin clusters when compared to placebo clusters, with just 25 samples per group (unpublished data).

We have used the measured difference in relative abundance of a specific macrolide ARG (ermX) 3.5 years after mass-azithromycin administration (unpublished data) as a medium effect size that maybe clinically relevant (Δ = 0.505). Using the approach for microbiome studies, accepting 90% power and 5% type I error (95% confidence interval),

NP Resistome Study

Version 5.0 21/05/2025

Page 15 of 30

we've calculated that we will require a sample size of 83 participants in each group to detect this effect size, using the formula $n=2(Z_{1-\alpha/2}+Z_{1-\beta})^2/\Delta^2$ [25].

In total we aim to recruit 350 study participants: 83 healthy community participants, 92 participants with pneumonia in the community, 92 participants admitted to hospital with pneumonia and 83 participants re-admitted to hospital with pneumonia. Study groups with a sample size of 92 participants permit a 10% loss to follow up.

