2.7.3.7 Inclusion criteria for children re-hospitalised with pneumonia

- Child aged between 12-24 months.
- Presence of all of the following symptoms: fever, cough, difficulty in breathing and fast breathing.
- Participant has been prescribed antibiotics for treatment of a lower respiratory tract infection on this presentation.
- Hospital admission to ANY hospital with a lower respiratory tract infection within the past 3 months.

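### The forecast of 90 re-admission cases applies a 6-month rate to a 3-month case definition; on the same inputs about 42 to 47 cases are expected against a target of 83

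*Protocol*

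**What the plan says.** Section 2.5 sets the case group at "83 participants re-admitted to hospital with pneumonia", from a calculation with standardised effect 0.505, 90% power and 5% type I error that gives 83 per group.

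Section 2.7.3.7 defines the case window: "Hospital admission to ANY hospital with a lower respiratory tract infection within the past 3 months". Section 2.1 uses the same 3 months, pneumonia after pneumonia.

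Section 2.15.1 names finding enough such children as a major challenge and builds its forecast in three steps:
- Volume of the earlier hospital study: "A study conducted at QECH between April 2013 and August 2016 recruited 1600 children presenting with pneumonia".
- Annual supply: "we could expect to recruit approximately 500 children hospitalised with pneumonia in a 12-month period".
- Re-admission rate, borrowed from severe anaemia: "with a readmission rate of 18% over 6 months", giving the forecast: "18% over 6 months, this would equate to just 90 cases in a 12-month period".

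The planned check is an audit: "A 4-week audit of hospital re-admission rates of children aged 12-24 months with pneumonia will be conducted at QECH before starting study recruitment". Secondary objective 1 in section 1.3.3 measures the re-admission rate "over a 4-week period in a single tertiary referral hospital in Malawi". Section 2.15.1 also lists fallbacks if enrolment is low in the first 4 months: a wider age range, a case to control ratio of 0.75 to 2, or a broader case definition.

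**The concern.** The 90 counts children re-admitted within 6 months. The case group admits only those re-admitted within 3 months, and no conversion is made. The slip matters because 90 lies just above 83: the target looks tight but reachable, whereas the 3-month figure falls well short of it.

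Re-hospitalisation is the adverse outcome named in the third primary objective, and the comparison of re-admitted with not re-admitted children is the study's test of it. If roughly half the cases arrive, that comparison does not have its planned power, and the conditional logistic regression of section 2.9.2, which adjusts for at least four confounders, rests on far fewer cases than intended. The risk section exists to size this risk and understates it.

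**Working it through.** **Inputs.** 500 admissions a year, 18% over 6 months, 1600 children from April 2013 to August 2016 (41 months), all from section 2.15.1. Target 83, effect 0.505, 90% power, 5% type I error, from section 2.5. Recruitment of 18 months with a 6-month community phase first, from section 2.4, leaving 18 − 6 = 12 months for the hospital.

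**The plan's own figures reproduce.**
- Forecast: 500 × 0.18 = 90.
- Sample size: 2 × (1.960 + 1.282)² / 0.505² = 82.4, rounded up to 83. Power at 83 v 83 is 90.2% (two-sided, normal approximation).

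**Conversion to 3 months.**
- Even spread: 0.18 / 2 = 9.0%; 500 × 0.090 = 45.
- Constant hazard: 1 − 0.82^0.5 = 9.45%; 500 × 0.0945 = 47.
- Annual volume implied by the earlier study: 1600 / 41 × 12 = 468. This gives 468 × 0.090 = 42 and 468 × 0.0945 = 44.
- Two-thirds of re-admissions in the first 3 months (assumption): 0.18 × 2/3 = 12%; 500 × 0.12 = 60 and 468 × 0.12 = 56.
- Needed for 83 cases: 83 / 500 = 16.6%, and 16.6 / 18 = 92% of the 6-month re-admissions; at 468 a year, 83 / 468 = 17.7%, and 17.7 / 18 = 98%.

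On the first two assumptions the yield is 51% to 57% of the target (42/83 to 47/83).

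**Power and detectable effect.** Power = Φ(0.505 / √(1/n₁ + 1/n₂) − 1.96). The effect detectable with 90% power is 3.24 × √(1/n₁ + 1/n₂).

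| Cases v controls | Power at 0.505 | Effect detectable at 90% power |
|---|---|---|
| 83 v 83 | 90% | 0.50 |
| 60 v 83 | 85% | 0.55 |
| 47 v 83 | 79% | 0.59 |
| 45 v 83 | 78% | 0.60 |
| 44 v 83 | 77% | 0.60 |
| 47 v 125 (ratio 0.75 to 2) | 84% | 0.55 |
| 44 v 117 (ratio 0.75 to 2) | 81% | 0.57 |

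At the 0.75 to 2 ratio, 90% power needs about 57 cases, above the 42 to 47 forecast.

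**Audit.** 500 × 4 / 52 = 38 admissions; fewer if children aged 12-24 months are only a subset of the 500. At 9% to 9.45% it would see 3 or 4 re-admissions; at 16.6%, about 6. Exact (Clopper-Pearson) 95% intervals:
- 3/38: 1.7% to 21.4%
- 4/38: 2.9% to 24.8%
- 6/38: 6.0% to 31.3%
- 7/38: 7.7% to 34.3%

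Each contains both 9% and 16.6%. For 4/38 the interval corresponds to about 15 to 124 cases a year.

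**The case against.** The strongest reply is that the protocol is candid. It calls case recruitment a major challenge, says no pneumonia re-admission data exist for the region, labels the 18% as a severe-anaemia figure, calls the source definition broader than its own, states the 90 conditionally, and lists three fallbacks. Rounding 468 to about 500 is a difference of some 6%. All of that stands, and it lowers the severity. It does not repair the window: none of the disclosures says that the rate covers twice the period that defines a case.

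Three stronger readings are tempting and are not supported.
- **That the sample size calculation is wrong.** It is not. It reproduces and does not depend on the forecast.
- **That 42 to 47 is a ceiling.** It depends on when re-admissions occur, which the protocol does not give; early clustering raises it. Prior admission to any hospital qualifies, so cases need not come from this hospital's own earlier admissions, and the 1600 were recruited children, who may be fewer than all those admitted. Against that, the broader source definition, the exclusions and the absence of a stated 12-24 month restriction push the other way. The age mix is not given, so no number can be put on that last point.
- **That the audit could never reveal a shortfall.** It also observes admission volume, and 0 or 1 re-admissions in 38 would exclude 16.6% (upper limits 9.3% and 13.8%). But at a true rate of 9.45% the chance of 0 or 1 is only about 11%, so imprecision is the fair criticism.

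Secondary objective 1 is openly a 4-week, single-hospital measurement and claims no precision. Its short window is a limitation to report, not an error.

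**Conclusion.** The mismatch is real and should be fixed. On the protocol's inputs, 12 months of hospital recruitment would give about 42 to 47 cases under an even spread or constant hazard, 56 to 60 if two-thirds of re-admissions come early, and 83 only if nearly all do. Nothing in the protocol supports the last. Ninety per cent power for the case-control comparison is therefore unsupported; with 44 to 47 cases and a full 83 controls it is 77% to 79%, and the effect detectable at 90% power rises from 0.505 to 0.59-0.60. This is a moderate loss: a reader might infer that the comparison is hopeless, and these figures do not say so.

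The result rests on the severe-anaemia rate as a proxy for pneumonia, on the annual volume in section 2.15.1, and on the timing assumption. Given the disclosure and the fallbacks, this is a point that should be fixed rather than one that invalidates the design.

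**What to change.** - In section 2.15.1, replace the 90 with the 3-month estimate, its range and the timing assumption behind it: 42 to 47 under even spread or constant hazard, 56 to 60 if two-thirds come early.
- State power and detectable effect at plausible case numbers, for example 83, 60 and 45, and for the 0.75 to 2 fallback at the corrected forecast (47 v 125: 84%; 44 v 117: about 81%).
- Start the 4-month enrolment review from the beginning of hospital recruitment. Section 2.4 puts community recruitment first, so a review counted from the study's start could fall before any case can be enrolled.
- Report the audit rate with its confidence interval, and also tally 3-month re-admissions among all children screened during hospital recruitment.

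The cost is a protocol amendment, a less favourable stated power for this comparison, and some extra recording by staff who already screen admissions; the protocol describes no existing log that would supply the tally.

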2.15.2 Recruitment of critically unwell patients

Where appropriate, we will seek to enrol critically unwell patients in the study, as data from these participants is key to understanding the impact of AMR on health outcomes. However, there may be times when it is not appropriate to approach a parent/legally acceptable representative to discuss participant enrolment, for example during emotional distress. Importantly, participant enrolment will never interrupt or disrupt provision of medical care to an acutely unwell patient.

2.15.3 Perception bias

To ensure voluntary study participation and avoid participant enrolment driven by the perception that patients will receive better care if enrolled in the study, the ICF will clearly explain to parents/legally acceptable representative s of participants that participation and/or withdrawal from the study will not affect the standard of care they will receive.

2.15.4 Challenges to identifying the legally acceptable representative for consent process

It may be difficult to identify the appropriate legally acceptable representative to consent for a child's participation in the study. The adult accompanying a potential participant

NP Resistome Study

Version 5.0 21/05/2025

Page 24 of 30

to a study enrolment site (i.e. Ndirande healthcare centre, GPCC or QECH) will be asked whether they are the child's parent; if not, they will be asked to identify the child's parent to obtain consent for study participation. If the child does not have a parent able to consent on their behalf, the accompanying adult will be asked to identify the child's legally acceptable representative to obtain consent for study participation. If no legally acceptable representative can be identified for the consent process, the child will not be enrolled in the study.

